## 4. Names and intended use of devices

## 4.1 Hybrid Closed Loop System:

The intervention arm will use the MiniMedTM 670G insulin pump, coupled with a 4th generation glucose sensor and GST3C transmitter. The closed loop algorithm is contained in the MiniMedTM 670G insulin pump, using a modified proportional integrative derivative (PID) model, with insulin feedback and additional safety features. The algorithm receives CGM data every 5 minutes, and a "basal rate" insulin delivery is computed and adjusted every five minutes. Therefore, standard "basal" insulin that is pre-programmed in regular insulin pump therapy is replaced by the algorithm derived insulin delivery (given as a micro-bolus every 5 minutes). Meals will still be announced, and an insulin bolus delivered according to the

HCL outpatient Version Number: 6.0 Version Date: 15/07/2019 individualised patient carbohydrate ratio and insulin sensitivity factor (should a correction bolus be required in addition to the insulin for carbohydrate).

#### 4.2 Blinded CGM

Blinded CGM will be collected three times during the study (baseline – at visit 3 for three weeks, midpoint – prior to visit 11 for two weeks, and prior to end for 3 weeks). A 4th generation sensor will be inserted and a GST3C connected. If there is any technical reason for the CGM data not being available for the minimum amount, participants will be offered additional CGM collection to meet the requirements of the protocol. Participants will be required to record finger prick glucose levels at least twice a day. CGM data is collected by uploading the GST3C and finger prick values from the CONTOUR® NEXT LINK 2.4 from Bayer.

# 4.3 Glucose monitoring

All participants will be issued with the CONTOUR® NEXT LINK 2.4 from Bayer. This glucose monitor requires CONTOUR PLUS test strips. For participants randomized to HCL, this allows for data to be directly sent to the insulin pump. For participants not on HCL, the CONTOUR® NEXT LINK 2.4 will be used in addition to their regular meter during CGM collection.

#### 4.4 Carelink Software

Carelink is a Medtronic web based platform which is used for uploading insulin pump data. The Medtronic 670G can be uploaded, using the CONTOUR® NEXT LINK 2.4, which is plugged into the USB port of a PC. The software is Apple and Windows compatible. Insulin pump data is then accessible for download by the investigators.

# 5. Hypothesis of the randomized controlled trial

HCL will increase time in sensor glucose target range (3.9 - 10 mmol/L) compared to standard therapy (CSII and MDI) by 10% (11). HCL will also reduce time spent hypoglycaemic by 60% (<3.9 mmol/L).

HCL outpatient Version Number: 6.0 Version Date: 15/07/2019

# 6. Study rationale, objectives and endpoints

# 6.1 Study rationale

Hybrid closed-loop insulin delivery, with automatic glucose sensing and insulin delivery reducing patient intervention, offers the potential to circumvent the significant glycaemic excursions associated with conventional therapy. Superior glucose control has been demonstrated along with lower rates of hypoglycaemia in many in-clinic studies, diabetes camp studies, hotel studies (12), and now in the first emerging short term outpatient studies (13-15) (including our pilot data). As such, closed-loop insulin delivery looks able to revolutionize T1D therapy. In hybrid closed loop systems, meals are still announced and bolus insulin is delivery according to the patient's individualised carbohydrate ratio, and insulin sensitivity.

We have recently conducted pilot studies using the Medtronic hybrid closed loop system and initial home studies have shown promise of its potential for more prolonged controlled trials (16).

The primary rationale is to quantify glycaemia with the use of the HCL system versus standard therapy (either MDI or CSII), including time in target range, as well as glycaemic excursions either hypoglycaemia or hyperglycaemia. We will explore the impact of this system on fear of hypoglycaemia and quality of life and other psychological measures. We seek to quantify the economic impact of HCL compared to standard therapy for translational purposes.

Vascular complications are a major cause of morbidity and premature mortality in people with diabetes, contributed to by a mix of traditional and novel vascular disease risk factors. Traditional risk factors include adiposity, dyslipidaemia, hypertension, smoking and poor glycaemic control. Novel vascular disease risk factors include subtle changes in lipoproteins, such as oxidation and non-enzymatic glycation, Advanced Glycation End Products (AGEs), oxidative stress, inflammation, altered angiogenesis, prothrombotic tendencies, glycaemic variability, impaired vasoregulation, and more recently recognised molecular changes. Molecular changes include telomere length, activity of telomerase (the enzyme which controls telomere length), microRNAs and DNA methylation.

Collection of suitable samples and their analyses are particularly relevant to this study as vascular damage starts early in life, particularly in people with Type 1 diabetes, better metabolic control may at least partially reduce adverse risk factor profiles and as yet unexplained residual risk remains in people with diabetes even when all traditional risk factors are controlled. Furthermore, we have cross-sectional data demonstrating improved vascular function and a less adverse novel vascular risk profile in insulin pump treated Type 1 diabetic patients and evidence that molecular markers can be improved by existent and emerging drug therapies.

This study will be conducted in 5 tertiary paediatric diabetes centres in Australia. They are Perth Children's Hospital, Perth; The Children's Hospital at Westmead, Sydney; John Hunter Children's Hospital, Newcastle; Royal Children's Hospital, Melbourne; and Women's and Children's Hospital, Adelaide. A home visit may be offered for some visits which involve insertion of blinded sensors prior to randomisation, mid and end of the study. This provides a patient centric approach working within the parameters of local policies and procedures on home visits. A All sites have a large cohort of patients with T1DM with a significant proportion of insulin pump usage, and have recent experience with a multi-centre clinical trial. This will support recruitment targets, allowing timely progression through the study. Also we may use advertisements, notices, and/or media to

HCL outpatient Version Number:6.0 Version Date:15/07/2019 recruit subjects. Examples include flyers posted in public settings, newspaper ads, and radio and television advertisement. All advertisements and recruitment materials (e.g., video, audio, and telephone scripts) will be submitted to HREC for prior approval.

# **6.2 Study Objectives**

## 6.2.1 Primary Objective:

The primary objective is to compare the proportion of time spent in target glycaemic range (sensor glucose level 3.9 - 10 mmol/l) while using HCL or using standard therapy (MDI and CSII).

# 6.2.2 Secondary Objectives:

The secondary objectives are to compare the efficacy of the MiniMed™ 670G Insulin Pump Hybrid Closed Loop System versus standard therapy (MDI and CSII) by the measurement of the following:

## 1. Glycaemic(24hr, day (0600 – 2400), night (0000 – 0600))

CGM data will be collected in three time blocks; baseline (3 weeks CGM), 13 weeks (2 weeks CGM) and 26 weeks (3 weeks CGM) post randomisation. A sub analysis of HCL vs. MDI and HCL vs. CSII is planned.

#### i. CGM data:

- a. % CGM Time < 2.8 mmol/L
- b. % CGM Time <3.3 mmol/L
- c. % CGM Time <3.9 mmol/L
- d. % CGM Time 3.9-7.8 mmol/L
- e. % CGM Time >10.0 mmol/L
- f. % CGM Time >13.9 mmol/L
- g. % CGM Time >16.7 mmol/L
- h. Standard Deviation and Coefficient of Variation of CGM values
- i. Mean CGM glucose
- ii. Average Fasting blood glucose (mmol/L), as measured during the three CGM time blocks at baseline, 13 weeks and 26 weeks. Defined as fasting capillary blood glucose level on waking (between 5am and 9am), at least 6 hrs after an insulin bolus for carbohydrate.
- iii. Average Glycaemic control as measured by HbA1c collected at baseline, 13 weeks and 26 weeks post randomisation.
- iv. Hospitalisations rate for diabetic ketoacidosis over the 7 month study period.
- v. Episodes of severe hypoglycaemia over the 7 month study period (defined having altered mental status and cannot assist in their care, is semiconscious or unconscious, or in coma ± convulsions and may require parenteral therapy (glucagon or i.v.glucose).

#### 2. Clinical measures

The compare the difference between HCL insulin delivery vs standard therapy for the following measures

HCL outpatient Version Number:6.0 Version Date:15/07/2019

- i) Change in auxological parameters (height, weight, BMI)
- ii) Change in total daily dose, including basal and bolus proportion, carbohydrate ratios and insulin sensitivity

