## 2. *Clinical*:

The difference between HCL insulin delivery vs standard therapy for the following measures

- i) Auxological parameters (height, weight, BMI)
- ii) Insulin delivery: total daily dose , including basal and bolus proportion, carbohydrate ratios and insulin sensitivity

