# 7 Design of the randomized controlled trial

# 7.1 Statement of design and randomisation

This is a prospective, randomized multi-centre study in adult and paediatric subjects from Australia, with type 1 diabetes mellitus aged 12 – 25 years. Participants can be on CSII or MDI treatment regimens to be eligible. After a run-in phase, subjects will be randomly assigned to one of the following two arms:

HCL arm: MiniMedTM 670G for 6 months; OR Conventional arm: MDI or CSII for 6 months.

Randomization will be stratified based on 4 variables: Time spent in target sensor glucose range (3.9 – 10mmol/L) – with participants evenly split above and below 55%(17) time in target range, age, diabetes duration, and centre site. This will be managed by the Clinical Trials Centre in Sydney.

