# Sensitivity analysis

The primary endpoint analysis will be re-run with the PP population as a sensitivity analysis. Secondary endpoints.

Coefficient of variation will be reported for each group: bootstrap methods will be used to estimate variability as appropriate.

Rates of hospitalisations for severe hypoglycaemia and moderate hypoglycaemia as per participant log will be analysed as unadjusted incidence rates based on the Poisson distribution. Incidence rates and incidence rate differences will be presented with their associated 95% confidence intervals calculated as exact Poisson confidence limits(22). In addition, where

HCL outpatient Version Number:6.0 Version Date:15/07/2019 appropriate Poisson or negative binomial regression models will be fitted e.g. moderate hypoglycaemia events from the participant log. If there are a high proportion of zero counts, zero inflated Poisson (ZIP) or zero inflated negative binomial models (ZINB) will be considered. If counts are sparse then rates will be reported descriptively only. Number of hospitalisations due to diabetic ketoacidosis events and other safety outcomes will be tabulated and presented as n and %.

Continuous outcome measures (including psychosocial) collected at baseline and endpoint will be analysed using ANCOVA adjusting for baseline score and site. Measures collected at baseline, 3 months and endpoint (e.g. *HbA1c*, *Fasting capillary blood glucose*, *Mean CGM glucose*, *Hypoglycaemic Fear Survey-II Worry scale*, *Child State-Trait Anxiety Inventory*, *The Diabetes Treatment Satisfaction Questionnaire status and change version*, *Problem Areas in Diabetes, Impaired awareness of hypoglycaemia: GOLD SCORE, INSPIRE questionnaires*) will be analysed using mixed models repeated measures (MMRM) adjusting for baseline score (where appropriate), group, period (baseline, 3 months, 6 months) and site. A random intercept term for 'individual' will also be employed if deemed appropriate. Least square means and least square mean differences and their associated 95% confidence intervals will be presented for each group and between groups. Unstructured covariance matrix will be used unless other covariance structures are more appropriate as determined by the Bayesian information criteria (BIC). Human technology interaction and health care professional experiences and expectations analyses will be reported Exploratory; descriptive analysis.

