## 7.4 Inclusion and exclusion criteria

## 7.4.1. Inclusion criteria:

- 1. Type 1 diabetes (diagnosis consistent with American Diabetes Association Classification of Diabetes Mellitus) diagnosed at least 1 year ago
- 2. Fasting C-peptide <0.1 nmol/L (in the absence of hypoglycaemia) within the last 3 months
- 3. Insulin regimen either:
  - Multiple daily injections (MDI) with  $\geq 4$  injections per day ( $\geq 3$  rapid-acting insulin and ≥1 long-acting insulin); or
  - Insulin pump therapy (CSII) established for  $\geq 3$  months
- 4. Aged 12-<25 years
- 5. HbA1c ≤10.5%
- 6. Living in an area with internet and cellular phone coverage
- 7. English speaking

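### The models for height and weight leave out age and sex in a cohort that mixes growing and fully grown participants, so the height comparison is less precise than the collected data allow.

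*Protocol*

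**What the plan says.** - **Outcome.** Section 6.2.2 (Clinical measures) sets a comparison of the arms on "Change in auxological parameters (height, weight, BMI". The matching endpoint in section 6.3 reads "Auxological parameters (height, weight, BMI". The synopsis lists height and weight only. No standard deviation score or percentile appears anywhere in the protocol.
- **Population.** Section 7.4.1: "Aged 12-<25 years".
- **Models.** Section 7.3 says that continuous measures taken at baseline and endpoint "will be analysed using ANCOVA adjusting for baseline score and site". Measures also taken at 3 months get a mixed model "adjusting for baseline score (where appropriate), group, period (baseline, 3 months, 6 months) and site". Auxology is named under neither. The visit schedule measures it at screening, randomisation, week 13 and week 26, so on the plain reading one of these two general rules covers it. Neither contains age or sex.
- **Allocation.** Section 7.1: "Randomization will be stratified based on 4 variables". Age is one of the four; sex is not.
- **Data at hand.** Date of birth and gender are recorded at Visit 1.

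**The concern.** Over 26 weeks a 12-year-old may gain several centimetres in height and a 24-year-old none. Age and sex predict most of that difference. The baseline value does not replace them: a girl and a boy of the same height and age can be at quite different stages of growth. A model with only baseline and site leaves this predictable spread in the residual.

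Age is also balanced at allocation but left out of the analysis. The standard error then still counts age variation that the design has already removed from the contrast.

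What is at stake is how closely the trial can estimate, or exclude, an effect of the closed-loop system on height. No hypothesis in the protocol concerns body size, and the primary endpoint is not involved.

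**Working it through.** The protocol states no SD, effect or power for auxology, so there is no figure of its own to reproduce.

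**Inputs from the protocol**
- Evaluable participants: 64 per arm, 128 in all (section 7.2; 80 enrolled per arm with 20% drop-out, 80 × 0.8 = 64).
- Five sites (section 6.1), 26-week follow-up, ages 12 to under 25.

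**Assumed inputs**
- Age uniform over 12–25, half the participants male.
- The 26-week height gain falls linearly from a peak at age 12 to zero at 16 (girls) or 18 (boys), with peaks of 1.5, 2.5 and 3.5 cm.

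**Height, first simulation.** 3,000 trials per scenario, measurement error SD 0.3 cm at each visit, individual variation in growth tempo, site not simulated. Mean standard error (SE) of the arm difference, in cm:

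| Peak gain | Baseline only | + linear age and sex | + age-by-sex growth terms |
|---|---|---|---|
| 1.5 | 0.119 | 0.097 | 0.085 |
| 2.5 | 0.168 | 0.124 | 0.097 |
| 3.5 | 0.217 | 0.155 | 0.114 |

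The variance ratio is the squared ratio of the SEs.
- Against the age-by-sex model: (0.119/0.085)² = 2.0; (0.168/0.097)² = 3.0; (0.217/0.114)² = 3.6.
- Against linear age and sex: (0.119/0.097)² = 1.5; (0.168/0.124)² = 1.8; (0.217/0.155)² = 2.0.

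In the middle case the 95% half-width is 1.96 × 0.168 = 0.33 cm as planned and 1.96 × 0.097 = 0.19 cm with the age-by-sex terms.

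**Height, second simulation.** Same peaks, five sites in every model, and a residual SD of 0.5 to 1.0 cm within age and sex. The extremes are:
- Peak 3.5 cm, SD 0.5 cm: SEs 0.200 (planned), 0.136 (linear), 0.092 (age-by-sex). Ratios (0.200/0.092)² = 4.7 and (0.200/0.136)² = 2.2.
- Peak 1.5 cm, SD 1.0 cm: SEs 0.197, 0.187, 0.184. Ratios (0.197/0.184)² = 1.15 and (0.197/0.187)² = 1.1.

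**False-positive rate for height (nominal 0.05).** In the first simulation the baseline-only model gave 0.039 to 0.051 without age balance. With allocation balanced on age (split at 16, an assumption) it gave 0.007 to 0.014. The test is not anti-conservative; with age balanced but unmodelled it becomes conservative.

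**Weight and BMI.** If the age-driven change falls linearly from a peak k to zero, and a share p of participants is still growing, its variance is k² × (p/3 − p²/4).
- p = (4/13 + 6/13)/2 = 0.385, so the bracket is 0.1282 − 0.0370 = 0.0912.
- SE ratio = √(1 + 0.0912 k²/s²), where s is the SD of individual change.
- Weight, k 1.5–3.5 kg, s 1.5–3.5 kg: lowest √(1 + 0.0912 × 2.25/12.25) = 1.01; middle (2.5, 2.5) 1.05; highest √(1 + 0.0912 × 12.25/2.25) = 1.22.
- BMI, k 0.2–0.6, s 0.6–1.2 kg/m²: lowest 1.00; middle (0.4, 0.8) 1.01; highest √(1 + 0.0912) = 1.05.

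This formula ignores whatever share of growth the baseline value already explains, so it does not understate the gain.

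**The case against.** The other side has a good case on several points.

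- **Scale.** The protocol never says that the analysis is on raw measurements, and an unseen analysis plan could define standardised scores. That is so. But section 7.3 does state a covariate set for continuous secondary outcomes. Adding age and sex changes a stated method; it does not fill in detail that a protocol normally defers.
- **Bias.** A reader might infer that normal growth contaminates the estimated effect, mixes with a change in adiposity, or yields false positives. The documents do not support this. The comparison is between randomised arms, growth is expected equally in both, and age is an allocation factor under section 7.1. The simulated false-positive rates agree.
- **Reach.** A reader might extend the point to all three measures. The figures do not allow that: the gain is negligible for BMI and small for weight.
- **BMI subgroup.** A reader might also fault the single set of BMI cut-points used at every age in the section 7.3 subgroups. Those groups are optional and labelled exploratory, and no age confounding has been quantified. They are no part of this point.
- **Size.** The height figures rest on growth curves that the protocol does not give. This stands, and it is why the range is wide. With small gains and a large residual SD the loss is only about 10 to 15% in variance.
- **Importance.** Auxology is an unpowered secondary outcome. This also stands.

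**Conclusion.** The point holds as a loss of precision, chiefly for height. Under assumed peak 26-week gains of 1.5–3.5 cm and residual SDs of 0.5–1.0 cm, the planned model gives a variance for the arm difference in height of about 1.2 to 4.7 times that of a model with age-by-sex terms, and about 1.1 to 2.2 times that of one with linear age and sex. For weight the SE is 1% to 22% larger than it need be; for BMI, 0% to 5%. These sizes depend heavily on the assumed growth curves. The direction does not: leaving out strong, recorded predictors of the outcome widens the interval. There is no bias and no excess of false positives, and the primary and glycaemic results are untouched.

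**What to change.** In section 7.3, state that the models for auxological outcomes, chiefly height and weight, also include age at randomisation, sex and their interaction, with age allowed to be non-linear (for example, piecewise terms over the growing years). Apply this whether the ANCOVA or the repeated-measures model is used.

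The cost is one sentence and no new data. With five sites the planned ANCOVA uses 7 parameters (intercept, arm, baseline, 4 site terms), leaving 128 − 7 = 121 residual degrees of freedom. Five further terms, as in the simulations, leave 128 − 12 = 116.

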### 3. Psychosocial:

Questionnaires will be conducted on 3 occasions: at baseline, 13 weeks and 26 weeks.

- **Fear of hypoglycaemia**: Hypoglycaemic Fear Survey-II Worry scale: 17-<25years. Children's Hypoglycaemia Fear survey 12 – 17 years.
- **Hypoglycaemia Awareness**: Hypoglycaemia Awareness Scale (Gold Score) (all ages) ii.
- **Anxiety**: State-Trait Anxiety Inventory (Child version for 12-15yrs, adult version ≥16iii. <25yrs)
- **Impact and Satisfaction**: The Diabetes Treatment Satisfaction Questionnaire status iv. and change version (16 - <25 years)
- Quality of Life: 12-<25 years: EQ-5D-Y, v.
- **Diabetes specific quality of life**: PedsQL –Child version (12 year olds), Adolescent vi. version (13-18) and young adult version (18-<25).
- **Diabetes distress:** Problem Areas in Diabetes (Teen version for 12 17 years, standard vii.  $version \ge 17 - <25 vr$
- Participant reported outcome for Automated Delivery system: INSPIRE viii. Questionnaires: baseline and post-assessment versions Child version (12 year olds), Adolescent version (13-18) and adult version(18-25)
- **Semi structure interview** (all ages post study, PCH only) ix.

# 4. Human-technology interaction:

To assess participant technology interaction and explore adherence patterns and approaches that may improve it. Repeated sampling methodology will be used. A series of questions will be asked once a week via a phone app, which will take less than 1 minute to complete.

#### 5. Health-economic

To assess the health economic impact of the MiniMed™ 670G Insulin Pump Hybrid Closed Loop System vs standard therapy (MDI and CSII). The following data points will be used as part of the economic analysis:

- i. QALYs calculated from the EQ-5D
- ii. Hypoglycaemic events and HbA1c
- Participant reporting on work interruption iii.
- Investigator reporting time spent on training, education and support, by the type of health iv. professional resource used
- Diabetes management consumables (glucose strips, ketone strips, batteries, sensors, site v. dressings, lancets, needles, insulin).

## 6. Biomarkers (all ages)

To assess the impact of the MiniMedTM 670G Insulin Pump Hybrid Closed Loop System Vs standard therapy (MDI and CSII) on the biomarkers listed below. Biomarkers will be tested from blood and urine samples at baseline, and 26 weeks post randomisation.

- Cell Adhesion Molecules (CAM)S i.
- Soluble vascular cell adhesion molecules sVCAM ii.

- iii. Soluble intercellular adhesion molecules sICAM
- s-e Selectin iv.
- Oxidized Low density lipoprotein v.
- Myeloperoxidase. vi.
- MicroRNA signatures for arterial, renal and retinal complications vii.
- **Telomerase** viii.
- ix. DNA methylation/acetylation
- Glycomark Χ.
- Isoprostanes and proteomics xi.
- Clotting profile xii.

## 7. Performance Parameters

To assess the performance of the MiniMedTM 670G Insulin Pump Hybrid Closed Loop System, and components. The following measures will be used:

- Proportion of time hybrid closed loop is active i.
- Unplanned exits from closed loop (n) ii.
- iii. Sensor performance – mean absolute relative difference (MARD), sensor failures (n)
- Insulin delivery line performance reported delivery line failures (n)iv.

